11.2 Study population

Intent to treat population

For the intent to treat (ITT) analysis all patients that have been randomized and start therapy will be included.

Per protocol population

Patients in the per protocol (PP) population for the primary efficacy analysis (PP1) are those that have received the study drugs and for whom the composite endpoint is available at baseline and after 1 year treatment, without major protocol violations.

For the secondary efficacy evaluation assessed as non-inferiority of DFP to DFX in terms of serum ferritin levels the PP population (PP2) includes only patients for whom the measure of serum ferritin is available at baseline and after 1 year treatment.

For the secondary efficacy evaluation assessed as non-inferiority of DPF to DFX in terms of successfully chelated patients according to cardiac MRI T2* the PP population (PP3) includes only patients for whom the measure cardiac MRI T2* is available at baseline and after 1 year treatment.

Safety population

The population for the safety and tolerability analysis will include all patients having received at least one dose of study medication.

PK and PKPD population

The population for the pharmacokinetic and subsequent exploratory analyses (e.g. correlation between systemic exposure and ferritin levels) will include patients who have received the investigational drugs throughout the duration of the study (i.e., 1 year) and have had a blood sample collected for the assessment of drug concentrations in plasma.

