11.6 Efficacy evaluation

Primary efficacy

The primary efficacy evaluation will be based on a treatment success rate defined in Section 4.3 Primary endpoint. The primary analysis will be based on the PP1 population.

In addition, an ITT analysis will be performed to corroborate the findings. If no composite endpoint is estimable at 1 year treatment (unavailability of serum ferritin and/or MRI determination either at baseline or after 1 year treatment), the subject is considered a treatment failure in the ITT analysis. Non-inferiority will be assessed based on the two sided 95% confidence interval $[\delta_L, \delta_U]$ of the difference $\delta = p_1 - p_2$, being p_1 and p_2 the proportion of success in the n_1 and n_2 patients randomised to DFP and DFX arms, respectively. Non-inferiority will be claimed if δ_L is greater than -0.125. The two sided 95% confidence interval for δ will be estimated based on asymptotic normal approximation for the difference of two binomial probabilities as follows:

$$(p_1 - p_2) \pm Z_{1-\alpha/2} \sqrt{Var(p_1 - p_2)}$$

where Z_γ is the γ^{th} percentile of the standardised normal distribution and

$$Var(p_1 - p_2) = p_1(1 - p_1)/n_1 + p_2(1 - p_2)/n_2$$

If non-inferiority of DFP to DFX is established based on the PP1 population and the confidence interval for the null hypothesis of non-inferiority based on the ITT population is similar or the percentage of success for DFP is greater than that of DFX in magnitude, the hypothesis that DFP is superior to DFX in terms of the defined success criteria will be tested at the one-sided alpha level of 0.025. Superiority testing will be based on the ITT population. The rationale for superiority is justified by the known beneficial effects of DFP at the cardiac level.

Secondary efficacy

Efficacy measured through serum ferritin levels

Serum ferritin will be analysed as secondary measure of treatment efficacy. Serum ferritin is a well validated and clinically widespread surrogate measure of iron load, highly correlated with iron in the liver. It represents an easy to assess parameter in the paediatric population.

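### Non-inferiority rests on PP1 alone: early leavers drop out of the deciding analysis, and no consequence is stated if PP1 clears -12.5% and ITT does not

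*Combined protocol and SAP*

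**What the plan says.** Section 11.2 defines ITT so that "all patients that have been randomized and start therapy will be included". PP1 is narrower: patients who received study drug, "for whom the composite endpoint is available at baseline and after 1 year treatment, without major protocol violations".

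Section 11.6 then gives the two sets different roles: "The primary analysis will be based on the PP1 population", and "In addition, an ITT analysis will be performed to corroborate the findings". If the composite cannot be formed, "the subject is considered a treatment failure in the ITT analysis". The claim requires the lower limit of a two-sided 95% Wald interval for the difference in success proportions to exceed -0.125. The next step opens with "If non-inferiority of DFP to DFX is established based on the PP1 population". It allows a superiority test on ITT if the ITT interval "is similar or the percentage of success for DFP is greater than that of DFX in magnitude".

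Sections 9 and 11.13 both say that patients who stop early count as treatment failures, and neither names an analysis set. Reason 1 in Section 9 is unsatisfactory therapeutic effect. Section 11.13 presents its handling of incomplete data as conservative. Sections 4 and 11.12 size the trial on 310 evaluable patients out of 388 enrolled, allowing about 20% dropout.

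**The concern.** A patient withdrawn for unsatisfactory effect has failed treatment in the plain sense, and Sections 9 and 11.13 say so. That patient has no 1-year composite and so is not in PP1. The failure rule reaches the patient only through ITT, and ITT does not decide non-inferiority. The conservatism that Section 11.13 describes therefore does not protect the primary claim.

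Followed as written, the plan lets a non-inferiority claim stand while the failure-counted analysis misses the margin. Nothing in it says whether such a claim would be withdrawn, qualified or left as it is. In an open-label trial (Section 6.5) that should be settled before the data are seen.

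**Working it through.** **Inputs from the plan.** One-sided alpha 0.025, power 80%, success 67.5% (DFP) and 65% (DFX), 310 evaluable, about 20% dropout, 388 enrolled (Section 11.12); 194 per arm (Section 4); margin -0.125 and Wald interval (Section 11.6).

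**The plan's own figure.** n per arm = (1.960 + 0.842)² × (0.675×0.325 + 0.65×0.35) / (0.025 + 0.125)² = 155.9, so 156 per arm or 312 in total, against 310 stated. At 155 per arm the standard error is 0.0537, and power is Φ(0.15/0.0537 − 1.96) = Φ(0.834) = 79.8%. Enrolment is 310/0.8 = 387.5, rounded to 388. The sizing reproduces.

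**One worked trial.** Suppose 145 of 194 on DFP and 165 of 194 on DFX complete, with 98 and 107 successes.
- PP1: 98/145 − 107/165 = 67.6% − 64.8% = +2.7 points; standard error 5.38 points; lower limit 2.7 − 1.96×5.38 = -7.8. Passes.
- ITT: 98/194 − 107/194 = 50.5% − 55.2% = -4.6 points; standard error 5.06 points; lower limit -14.6. Fails.

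**How often this happens.** Assumptions: all 194 per arm start therapy; withdrawal is unrelated to response; completers succeed at the planned rates; PP1 is completers only; ITT is all 194 with withdrawals as failures. The withdrawal splits are assumed. 400,000 simulated trials per row.

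| Withdrawals DFP/DFX | PP1 passes | ITT passes | Both pass | PP1 passes, ITT fails |
|---|---|---|---|---|
| 20%/20% | 80% | 81% | 75% | 5% |
| 22.5%/17.5% | 80% | 60% | 58% | 22% |
| 25%/15% | 80% | 34% | 34% | 46% |
| 15%/25% | 80% | 99% | 80% | under 0.1% |

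The sets can also disagree the other way: ITT passes and PP1 fails in about 7% of trials at 20%/20% and 19% at 15%/25%.

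**False claims.** First set the failure-counted difference at exactly -12.5 points, with DFX completers at 65%. At 25%/15%, DFX succeeds in 0.65×0.85 = 55.25% of all patients. DFP must then succeed in 42.75%, which is 0.4275/0.75 = 57% of completers, a completer difference of -8 points. PP1 alone claims non-inferiority in 12.7% of trials, and requiring both sets in 2.2%. PP1 alone claims in about 3.1% at 22.5%/17.5% and 0.6% at 20%/20%.

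The reverse case matters too. With the completer difference at exactly -12.5 points, ITT alone claims in 6.9% of trials at 20%/20% and 38% at 15%/25%. Neither set is safe alone. Requiring both stayed at or below 2.5% in every case run.

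**The case against.** The strongest reply is that the plan has already chosen its set. Section 11.6 calls PP1 primary and later speaks of non-inferiority established on it. A reader might infer from the definition of n1 and n2 over "patients randomised to DFP and DFX arms, respectively" that the deciding set is ambiguous and could be picked afterwards. The text does not support that: Section 11.6 uses the same phrasing for the ferritin comparison, whose stated population is PP2, so it looks like stock formula wording. What is missing is the consequence of a discordant ITT result.

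A reader might also infer that Sections 9 and 11.13 flatly contradict the PP1 definition. They need not. Section 11.6 ties the missing-composite rule to ITT, and the 310-of-388 sizing fits a PP1 without early leavers. Leavers outside PP1 and failures in ITT is a coherent reading, but the two sections never state it.

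Nor does the loose superiority gate admit false superiority claims. Superiority is tested on ITT, and an ITT lower limit above 0 is already above -12.5%. That wording is an editorial matter.

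Two further points stand in part. The splits by arm are assumptions; if withdrawals are balanced, or as few as Section 11.13 expects, the PP1-only discordance is small. And nothing in the documents requires both sets to pass. The sponsor could keep PP1 alone and state in advance what a failed ITT means, but PP1 alone would then keep the 12.7% false-claim rate of the 25%/15% case if the failure-counted difference is the target.

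**Conclusion.** The concern holds as a missing decision rule plus unreconciled wording, and should be fixed. The sizing has no arithmetic error.

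Its size depends on how withdrawals divide between arms: PP1-only claims in about 5% of trials if balanced at 20%, 22% with a 5-point excess on DFP, and 46% with a 10-point excess. The 12.7% at 25%/15% is an error rate only if the failure-counted difference is what the trial should estimate.

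It would be tempting to conclude that the PP1 analysis favours DFP. The documents do not support that. They give no dropout by arm, and the text points both ways: Section 11.13 suggests that DFX compliance may be even better, while reason 3 in Section 9 applies to DFX only. If withdrawals are heavier on DFX, PP1 is the harder test. The simulation models neither withdrawal for lack of effect nor PP1 exclusions for major violations, so it does not show how far those would move the figures.

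**What to change.** (a) In Section 11.6, state that non-inferiority is claimed only if the lower limit of the two-sided 95% interval is above -12.5% in both PP1 and ITT, with withdrawals and missing composites counted as failures in ITT. Test superiority on ITT only after that, in place of the present gate; this loses no superiority claim.

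(b) In Sections 9 and 11.13, name the set to which the failure rule applies. ITT matches Section 11.6 and the sizing, but the sponsor should confirm it. Say also how withdrawals for unsatisfactory effect enter PP1.

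(c) In Section 11.12, give joint power beside the PP1 power.

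**Cost.** Wording, and a lower stated power. Joint power at 194 per arm is about 75% instead of 80% with balanced 20% withdrawals, and about 80% with balanced 10%. It falls to 58% at 22.5%/17.5% and 34% at 25%/15%, the patterns in which the two sets disagree most. Restoring about 80% at balanced 20% would need about 220 per arm (440 in total, against 388). The recommendation is to restate the power and not to enrol more.

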7.2.5 Off-Study requirements**V16/month 13 follow up assessment or withdrawal visit**

CONFIDENTIAL

DEEP Consortium
DEEP2-Efficacy/Safety Study Protocol

Protocol No. DEEP-2

This visit should be completed one month (\pm 7 days) after Visit 15 or in case of withdrawal. The following assessments will be performed:

- Clinical physical examination
- Vital signs
- Concomitant medications
- Adverse events
- Body height/weight

In case of withdrawal, centralized serum ferritin and CHQ will be also assessed.

Additional information regarding clinical procedures will be provided in the SPM.

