9. INTERRUPTION OF TREATMENT

This section deals with a patient's premature withdrawal from the study before completing all scheduled visits. An individual subject may be withdrawn at the discretion of the responsible investigator and the study team for the reasons listed hereby. In the event one or more subjects are withdrawn, additional subjects may be enrolled to ensure an adequate number of subjects complete the cohort.

Reasons that a patient must discontinue participation in a clinical study are considered to constitute one of the following:

1. unsatisfactory therapeutic effect (quarterly increase in ferritin levels of at least 1500 ng/ml as detected by two determinations performed at no more than two weeks interval, or if cardiac MRI T2* decreases under 10ms)
2. subject's condition no longer requires study treatment
3. DFX treatment at 10 mg/kg/day (for safety reasons) for more than 4 weeks
4. DFP or DFX administration suspended (for safety reasons) for more than 4 weeks
5. adverse event(s) requiring change of chelation therapy, including moderate or severe Neutropenia
6. significant protocol violation
7. subject/legal guardian withdrew consent/assent
8. lost to follow-up
9. administrative problems
10. death

In the absence of a medical contraindication or significant protocol violation, the investigator may make an effort to keep the subject in the study. Should a subject withdraw or be withdrawn by the legal guardian, he/she has to complete a full set of the 'end-of-study phase assessments', i.e. a full V16 evaluation. Relevant records will have to be done on the corresponding CRF pages.

This requirement does not refer to patients who passed the screening and washout period and were found not to be eligible for treatment.

Patients prematurely withdrawn from the treatment will be considered treatment failures.

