Serum ferritin will be tested in terms of quantitative variable as part of the composite endpoint measurable in the entire experimental population. The purpose of this analysis is to clarify the interpretation of the primary composite endpoint and hence no adjustment for multiplicity will be considered. The population for this analysis is the PP2. ITT analysis will be used to corroborate the findings.

Non inferiority of DFP to DFX will be tested considering a non inferiority margin of 400 ng/mL.

Non-inferiority will be assessed based on the two sided 95% confidence interval $[\delta_L, \delta_U]$ of the difference $\delta = m_1 - m_2$, being m_1 and m_2 the mean difference between baseline and end of treatment assessments of DFP and DFX, respectively, and n_1 and n_2 the numbers of patients randomised to DFP and DFX arms. Non-inferiority will be claimed if δ_L is greater than -400 ng/ml.

The two sided 95% confidence interval for δ will be estimated as follows:

$$(m_1 - m_2) \pm Z_{1-\alpha/2} \sigma \sqrt{\frac{1}{n_1} + \frac{1}{n_2}}$$

where Z_γ is the γ^{th} percentile of the standardised normal distribution and σ^2 is the pooled variance.

Serum ferritin trends over the 1 year period of treatment will be also investigated. A repeated measures analysis of variance model with treatment-group as main effect will be fitted. The H_0 of equal between group regression slopes will be tested by evaluating whether the interaction between the categorical factor (treatment group) and the repeated measure (monthly measures of serum ferritins) equals zero, i.e. no interaction. The rejection of the null hypothesis on the interaction term (treatment group*monthly ferritin measure) will be supportive of different trends between DFP and DFX arms. The ITT population will be used for this analysis. Handling of missing data for this analysis is described in Section 11.4.

Descriptive statistics for trends in subgroups of patients according to age classes will be also provided.

Efficacy measured through cardiac T2* MRI

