In the last years, the role of cardiac MRI T2* in the management of patients affected by hereditary haemoglobinopathies has been highlighted. Findings are available for the adult population, more limited experience is reported in children. Despite the importance of early detection of cardiac siderosis, MRI is difficult to perform in the paediatric population and it is usually uninformative in younger children (namely less than 10 years) due to late iron accumulation in the heart.

As a consequence, cardiac MRI T2* will be analysed as additional secondary measure of treatment efficacy in the subgroup of patients (over 10 years) for which the scan is available. It will be analysed as binary variable (successfully/unsuccessfully chelated patient according to the criterion 4.3.1 in Section 4.3) as part of the composite endpoint as well as according to its quantitative nature.

Due to the paucity of paediatric data on cardiac MRI T2*, descriptive statistics will be calculated and used to support efficacy conclusions. Descriptive measures will be listed by visit and treatment and characterised by frequency and percentage or mean, standard deviation, median, and quartiles.

However, considering the importance of improving knowledge on iron overload at the heart level in the paediatric population, a test for non inferiority of DFP to DFX in terms of cardiac MRI T2* (successfully/unsuccessfully chelated patient according to the criterion 4.3.1 in Section 4.3 Primary endpoint) will be performed whenever MRI evaluation will be available in at least 60-70% of the evaluable population. See section 11.3 different scenarios (non inferiority margins and sample size) related to this secondary efficacy assessment. The population for this analysis is the PP3.

Efficacy measured through MRI liver iron concentration

Iron overload in the liver compartment will be assessed as additional secondary measure of efficacy. LIC changes within one year will be evaluated in terms of percentage of successfully chelated patients according to the success criterium described in section 4.4.1 Secondary endpoints. LIC absolute values will be also analysed.

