11.13 Handling of missing data

A negligible amount of missing data is expected in this study because the patient population under study (patients affected by haemoglobinopathies requiring chronic transfusion and chelation therapy), and their parents, are accustomed to routine close monitoring in clinical visits, are used to frequent lab tests and comply with uncomfortable examinations (MRI), and are generally willing to participate in trials that may lead to increasing the availability of treatments. Moreover, the estimated treatment effect is not expected to be importantly biased in favour of the experimental treatment due both to the choice of the comparator and of the primary endpoint.

DFX is an oral chelator as DFP, and its compliance is expected to be comparable to that of DFP, or even better taking into account the once a day administration.

The completeness of the data that will allow the estimate of the primary endpoint (percentage of successfully chelated patients) is expected to be high due to the type of patients and condition.

Finally, patients who prematurely discontinue the trial for any reason will be considered treatment failures.

Assuming the worst scenario for incomplete data in order to provide conservative estimates for the trial results, the imputation of missing data will only apply to missing data because of a missing visit. This will affect the trend analysis for the secondary evaluation on serum ferritin levels. In this case, Linear Mixed Models (LMM) will be used as imputation method for missing data.

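### The cardiac T2* non-inferiority test has no supporting ITT analysis, so patients withdrawn because T2* fell below 10 ms are left out of it instead of counting as failures

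*Combined protocol and SAP*

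**What the plan says.** Section 11.2 defines the population for the cardiac T2* test: "the PP population (PP3) includes only patients for whom the measure cardiac MRI T2* is available at baseline and after 1 year treatment". Section 11.6, after describing that test, adds "The population for this analysis is the PP3" and names no other population for it.

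The other two non-inferiority tests in Section 11.6 are handled differently. For serum ferritin: "The population for this analysis is the PP2. ITT analysis will be used to corroborate the findings". For the primary composite, the PP1 analysis is backed by an ITT analysis, and if the endpoint cannot be determined "the subject is considered a treatment failure in the ITT analysis".

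Section 9 lists unsatisfactory effect among the reasons for discontinuation, met by a large ferritin rise "or if cardiac MRI T2* decreases under 10ms". It closes with "Patients prematurely withdrawn from the treatment will be considered treatment failures". Section 11.13 says the same: "patients who prematurely discontinue the trial for any reason will be considered treatment failures".

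T2* scans are scheduled at baseline, month 6 and month 12 (Sections 4.4.2, 7.1 and 7.3.14). For the withdrawal visit, Section 7.2.5 states "In case of withdrawal, centralized serum ferritin and CHQ will be also assessed". No MRI is listed there or in the withdrawal note to Table 5.

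**The concern.** Whether a patient stays in PP3 can depend on the endpoint that PP3 is used to measure. The patients most clearly failing on cardiac iron at month 6 are the ones whose month-12 value will not exist. PP3 then estimates T2* success among patients who were not stopped early, which is a different quantity from T2* success among patients who started treatment.

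Section 4.4.2 gives the T2* analysis the task of clarifying the composite. If the arms lose different shares of patients, the T2*-alone comparison shifts in favour of the arm that loses more, and no parallel T2* analysis is planned to show this. Unequal loss is plausible. The trial is open label (Section 6.5) and the exit routes differ by arm. Section 9 has a low-dose discontinuation reason that applies to DFX only, and the renal dose reductions in Table 4 apply to DFX only. Section 8 refers to neutropenia induced by DFP, and moderate or severe neutropenia ends participation. These routes pull in opposite directions, so the documents do not say which arm would gain.

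**Working it through.** **Step 1: does the trigger imply failure?** Criterion B (Section 4.3.1) requires a patient with baseline T2* of 20 ms or more to stay at 20 ms or more, and a patient with baseline below 20 ms to rise by at least 10%. A fall to below 10 ms meets neither. Criterion B is formally judged after 1 year, so strictly the patient fails it on the scan that triggered withdrawal.

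**Step 2: is the patient lost from PP3?** The only scheduled on-treatment scan before month 12 is at month 6. After withdrawal on that scan, no later MRI is scheduled, so there is no 1-year T2* and the patient is outside PP3. A patient first found below 10 ms at month 12 stays in PP3 and is scored a failure. Any other withdrawal before month 12 also removes the patient from PP3.

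**Step 3: the plan's own figures.** Table 7, first scenario (DFX 65%, DFP 70%, margin 12.5 points, one-sided 0.025, 80% power):

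n per arm = [0.65×0.35 + 0.70×0.30] × (1.960 + 0.842)² / (0.125 + 0.05)² = 0.4375 × 7.849 / 0.030625 = 112.1, against 112 stated.

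The other three scenarios give 135, 102 and 123, as stated. The arithmetic of Table 7 is sound; the issue is the analysis population.

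**Step 4: false non-inferiority rate.** Assumptions: 112 patients per arm with a baseline scan (borrowed from Table 7), and a true difference exactly at the margin when withdrawals count as failures (DFX 65%, DFP 52.5%). The withdrawn shares w1 (DFP) and w2 (DFX) are also assumed, because the documents give no split by arm and no expected rate of T2* below 10 ms. Among patients left in PP3 the rates are p1 = 0.525/(1−w1) and p2 = 0.65/(1−w2), with n1 = 112(1−w1) and n2 = 112(1−w2). The chance of claiming non-inferiority is Φ[(p1 − p2 + 0.125)/SE − 1.96], where SE² = p1(1−p1)/n1 + p2(1−p2)/n2.

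Example, 10%/5%: p1 = 0.583, p2 = 0.684, difference −0.101, SE = 0.0667. Then Φ(0.362 − 1.96) = 5.5%.

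| Withdrawn DFP/DFX (assumed) | PP3 rates DFP/DFX | PP3 difference (points) | False claim |
|---|---|---|---|
| 0%/0% | 52.5/65.0 | −12.5 | 2.5% |
| 5%/5% | 55.3/68.4 | −13.2 | 2.0% |
| 10%/10% | 58.3/72.2 | −13.9 | 1.5% |
| 0%/5% | 52.5/68.4 | −15.9 | 0.65% |
| 2%/0% | 53.6/65.0 | −11.4 | 3.6% |
| 5%/0% | 55.3/65.0 | −9.7 | 6.2% |
| 10%/5% | 58.3/68.4 | −10.1 | 5.5% |
| 10%/0% | 58.3/65.0 | −6.7 | 13.9% |

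Counting withdrawals as failures gives 2.5% in every row. If the 65% for DFX is instead taken among scanned patients only, 10%/5% gives 5.1% and an equal 20%/20% gives 0.8%.

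**Step 5: the planning case.** With 70% and 65% success among patients who reach month 12, PP3 shows +5 points whatever the withdrawals. Counting withdrawals as failures, the difference is (1−w1)×70 − (1−w2)×65:

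- 5%/5%: 66.5 − 61.75 = +4.75, with power 77% against 78% in PP3.
- 20%/20% (the planned dropout, split equally): 56 − 52 = +4.0.
- 10%/5%: 63 − 61.75 = +1.25, with power 57% against 77% in PP3.
- 25%/15%: 52.5 − 55.25 = −2.75.
- 15%/25%: 59.5 − 48.75 = +10.75.

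**The case against.** The test carries limited weight. It is secondary, unadjusted for multiplicity, and run only if MRI is available in at least 60–70% of the evaluable population. Section 11.6 leans on descriptive statistics for T2* because paediatric data are scarce. All of this stands, and it limits the importance of the point.

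A reader might infer that the loss is invisible everywhere, or that it touches the primary conclusion. The documents do not support either reading. The composite ITT analysis counts these patients as failures, and superiority is tested in the ITT population. T2* descriptives by visit may also show the month-6 values, although it is unclear whether the PP3 restriction applies to them. Still, the composite mixes ferritin with T2*, so it cannot isolate the cardiac result.

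A reader might also infer that PP3 favours DFP or inflates the false-claim rate. That holds only if DFP loses more patients, which is an assumption; with equal loss PP3 is slightly conservative. Withdrawal for T2* below 10 ms may also be uncommon: a known T2* under 10 ms is an exclusion criterion, and the protocol says cardiac iron accumulates late in children. The scenarios above cover withdrawal for any reason.

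It can further be said that a per-protocol set normally requires the endpoint, that PP1 and PP2 do the same, and that Section 9 speaks of treatment failures in general, not criterion B failures. This is fair. But PP1 and PP2 are each backed by ITT, and the inclusion rule for PP3 removes withdrawn patients before any failure rule can act. Further detail may come in a later analysis plan, but nothing in the present text provides this analysis.

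**Conclusion.** The point holds as a gap in one secondary analysis. As written, the T2* test excludes patients who failed on T2* at month 6 and were withdrawn for it, and no ITT-type analysis stands beside it. The PP3 definition and the failure rule in Sections 9 and 11.13 need to be reconciled for this test.

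The size and direction of the bias cannot be determined from the documents. The range in the scenarios, from below 2.5% to about 14%, rests on assumed withdrawal splits, on 112 baseline-scanned patients per arm, and on treating every withdrawal as a failure. It shows sensitivity and does not forecast error. The documents do not support a stronger conclusion, such as an established bias towards DFP or a threat to the primary result. Label: cheap improvement.

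**What to change.** In Sections 11.2 and 11.6, add a supportive ITT-type analysis of criterion B in all treated patients aged 10 years or over with a baseline T2*. Report it beside PP3, in the same corroborating role that the ITT analysis has for ferritin.

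- Score patients withdrawn because T2* fell below 10 ms as criterion B failures, using the scan that triggered withdrawal.
- Score other withdrawals before month 12 as failures, in line with Sections 9 and 11.13.
- State how a patient who reaches month 12 without a scan is scored. The composite ITT rule in Section 11.6 already treats a missing MRI as failure and could be carried over.
- Tabulate withdrawals before month 12 by arm and reason among patients with a baseline T2*, so that any imbalance is visible.

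There is no need to require both intervals to lie above the margin. That would be stricter than the plan's own primary rule, where PP1 decides and ITT corroborates.

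Cost: a wording change and one extra analysis on data already collected, with no additional scans. Downside: the reported T2* success rates will be lower than in PP3, and scoring all withdrawals as failures can dilute a real difference when withdrawal is equal, which is why it should stand beside PP3 and not replace it.
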